11.2.4 ECG ASSESSMENT

All patients will have a 12-lead ECGs collected in triplicate and centrally read by a blinded independent cardiologist and QTc intervals, calculated and corrected using the Fredericia method (QTcF), at screening, baseline, the end of Week 4, the end of Week 12, the end of Week 24 or the end of treatment visit, and every 3 months while in the follow-up period (pre-dose only for the post 24-week follow-up visit and 30 days after the last dose of study treatment). Additional ECGs may have been collected in the event patient demonstrated QTc prolongation.

The three QTcF interval measures will be averaged for a summary measure of QTcF interval.

11.2.5 CARDIAC EJECTION FRACTION ASSESSMENT

All patients will have ejection fraction (echocardiogram or MUGA scan) at screening, the end of Week 4, the end of Week 12, the end of Week 24 or the end of treatment visit, and every 6 months while in the follow-up period, and 30 days after the last dose of study treatment.

11.2.6 ADDITIONAL SAFETY ASSESSMENTS

11.2.6.1 Vital signs including pulse, systolic and diastolic blood pressure, respiratory rate, temperature, and body weight.

11.2.6.2 Physical examination, including clinical signs and symptoms, and spleen measurement.

12 EFFICACY ENPOINTS AND ANALYSES

12.1 PRIMARY EFFICACY ENPOINTS

12.1 1 Spleen Volume Reduction

The primary efficacy variable for dosage selection is the percent reduction in spleen volume from baseline as measured by MRI or CT at Weeks 12 and 24..

Descriptive statistics of spleen volume at baseline, Week 12, Week 24, and at End of Treatment will be presented by treatment arm. Spleen volume at End of Treatment is defined as the spleen volume collected at the end of treatment visit or the last spleen volume measured on treatment if not measured at end of treatment. Descriptive statistics of percent reduction in spleen volume at Weeks 12 and 24 and at End of Treatment will be presented by treatment arm. These descriptive statistics include counts, mean, standard deviation, standard error of the mean, median, 25th percentile, 75th percentile, minimum, and maximum. As a supportive measure of efficacy, the counts and proportions of patients with spleen volume reduction (SVR) $\geq 35\%$ at Weeks 12 and 24 and at End of Treatment will be presented by treatment arm. The exact (Clopper-Pearson) 95% confidence intervals (CIs) for the proportions will also be presented. Additional supportive analyses include imputing missing Week 24 spleen volume with the previous post-baseline (Week 12) spleen volume, if any, and repeating the above analyses. These analyses will be repeated for spleen volume measured after Week 24 in long term follow up.

12.1 2 Total Symptom Score (TSS) Analysis

Descriptive statistics of individual symptoms and TSS at baseline, every 12 weeks, and at End of Treatment will be presented by treatment arm. Descriptive statistics of percent reduction in TSS every 12 weeks and at End of Treatment will be presented by treatment arm. The counts and proportions (including Clopper-Pearson 95% CIs) of patients with TSS reduction $\geq 50\%$ every 12 weeks and at End of Treatment will be presented by treatment arm. Supportive analyses include imputing missing Week 24 TSS with the previous post-baseline (Week 12) TSS, if any, and repeating the above analyses at Week 24.

As an anchor for patient-reported symptom assessment, the patient global impression assessment (PGIA) will also be summarized and evaluated for correlation with TSS. There is 1 domain in the PGIA instrument with possible scores ranging from 1 (very much improved) to 7 (very much worse).

12.1 3 Patient Global Impression Assessment

The scores for the PGIA will be summarized by treatment arm at each visit at which the patients are scheduled to complete the instrument using descriptive statistics. Additionally, the correlation between PGIA and TSS and the change in PGIA and change in TSS at each visit assessed will be explored.

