Patients who discontinue pacritinib treatment prior to Week 24, with or without disease progression, will continue to follow this Study Assessments Calendar through Week 24.

Patients who undergo splenic irradiation, splenectomy, or who initiate any non-protocol-directed anti-myelofibrosis treatment at any time must complete the *End of Treatment* visit within 7 days of stopping the drug and *30 Day Post End of Treatment* visit within 30 days of *End of Treatment* visit, but will not complete any additional visits.

If an arm is closed, patients randomized to that arm will end pacritinib treatment and complete the *End of Treatment* visit within 7 days of stopping the drug and *30 Day Post End of Treatment* visit within 30 days of *End of Treatment* visit.

Unscheduled visits should include physical examination, laboratory tests, and radiographic evaluations as clinically indicated in the judgement of the investigator and these results must be entered into the EDC.

Additional visits may be required for patients with baseline platelet count $\leq 50,000/\mu$ L as well as patients who have pacritinib dose modifications due to hematologic, cardiac, diarrhea, or other non-hematologic toxicities in addition to those specified in Section 6.5. Samples drawn for clinical laboratory assessments at unscheduled visits should be submitted to the central laboratory for analysis in addition to any local analysis that may be performed for the purpose of patient management. See Section 6.5 for details.

Abbreviations

Abbreviation	Full Term
AE	adverse event
ALT	alanine aminotransferase (syn: see SGPT)
ASCT	allogeneic stem cell transplantation
AST	aspartate aminotransferase (syn: see SGOT)
AUC	area under the curve
AUC _{inf}	area under the curve to infinite time
AUC _{0-t}	area of the curve up to the last measurable concentration
BAT	best available therapy
BID	twice per day
BUN	blood urea nitrogen
CBC	complete blood count
C _{max}	maximum concentration observed
C _{min}	minimum concentration observed
CRF(s)	case report form(s)
СТ	computed tomography
CTCAE	Common Terminology Criteria for Adverse Events
CYP450	cytochrome P450
DIPSS	Dynamic International Prognostic Scoring System
ECG	electrocardiogram
ECOG	Eastern Cooperative Oncology Group
eCRF	electronic case report form
EDC	electronic data capture
EPs	erythroid progenitors
ET	essential thrombocythemia
FAS	Full Analysis Set
FDA	Food and Drug Administration
FLT3	fms-like receptor tyrosine kinase 3

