3.3 Treatment Continuation After Progression of Disease

Patients who have progression of disease on MRI (preferred) or CT scan, defined as an increase in splenic volume of \geq 25% from baseline on MRI or CT scan, will not be allowed to continue study treatment. Patients should continue the visit schedule through Week 24 (including imaging and all protocol-specified study assessments) despite treatment discontinuation or disease progression prior to Week 24, unless patient withdraws consent, dies, undergoes splenic irradiation or splenectomy, or initiates any non-protocol-directed anti-myelofibrosis treatment.

4 Patient Selection and Withdrawal

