7.1.1.1 Spleen Volume

MRI is the preferred modality; CT scan will be used for patients who cannot undergo MRI, or for whom MRI is not available. Imaging should be performed without contrast agent. For each patient, the same imaging modality should be used throughout the study.

Spleen volume will be measured by MRI (preferred) or CT at screening and at the end of weeks 12 and 24 visits. Spleen volume will also be measured at the end of treatment if this does not occur at the end of

Week 24. For patients who continue on pacritinib past Week 24, spleen volume will be assessed by MRI or CT every 3 months up to 2 years. Patients who discontinue treatment (except withdraw of consent or death) will be required to complete the end of treatment visit within 7 days of stopping treatment. Unscheduled imaging studies may be performed at physician discretion if he/she considers disease-related symptoms to be worsening. All images generated as part of unscheduled evaluations must be submitted by the investigator for central review. An independent radiologist, blinded to all patient and site identifiers and treatment assignments, will measure spleen volume. While images generated as part of unscheduled visits may be read locally if treatment discontinuation is being considered, only the scheduled centrally read images will be used for the efficacy analysis.

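### The supportive Week 24 carry-forward for spleen volume uses the Week 12 scan even when a later, required End of Treatment scan exists

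*SAP*

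**What the plan says.** SAP 12.1.1 summarises percent reduction in spleen volume and the proportion with at least 35% reduction at Week 12, Week 24 and End of Treatment, by arm. It then adds a supportive repeat of these summaries after "imputing missing Week 24 spleen volume with the previous post-baseline (Week 12) spleen volume, if any". The donor scan is therefore Week 12 and no other. SAP 12.1.2 has the same Week 12 rule for a missing Week 24 TSS.

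The protocol provides a later measurement. Section 7.1.1.1 states: "Spleen volume will also be measured at the end of treatment if this does not occur" at Week 24. It adds that patients who discontinue, other than by death or withdrawal of consent, "will be required to complete the end of treatment visit within 7 days of stopping treatment". Protocol Table 1 lists spleen volume at that visit, so this is a scheduled scan. The SAP uses it in its own summary: "Spleen volume at End of Treatment is defined as the spleen volume collected at the end of treatment visit", with the last on-treatment scan as the fallback.

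Two further provisions matter:

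- Under Protocol 3.3, patients whose spleen volume has risen at least 25% above baseline on imaging "will not be allowed to continue study treatment".
- Under the special cases that follow Protocol Table 1, patients who have splenic irradiation or splenectomy, or who begin other anti-myelofibrosis treatment, attend the End of Treatment and 30-day visits "but will not complete any additional visits".

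**The concern.** Carrying a value forward is normally meant to use the most recent valid measurement. Here the rule names a fixed visit. A patient can respond at Week 12, regrow, be scanned at End of Treatment, switch therapy, and then appear in the carried-forward Week 24 table with the Week 12 volume. The later scan has already been acquired and is eligible for central reading, so nothing is gained by leaving it out.

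Percent reduction in spleen volume is the primary efficacy variable for dosage selection, and no hypothesis is tested, so readers will compare the by-arm summaries directly. For the continuous variable, the carry-forward is the only analysis in which the SAP fills in a missing Week 24 value. A reader would take it as the check on the observed-case mean, and for these patients that check does not use the best information held.

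**Working it through.** **Which scans can enter.** The SAP analysis windows for spleen volume are Days 63 to 105 (Week 12) and Days 147 to 189 (Week 24). Days 106 to 146 belong to neither: 146 − 106 + 1 = 41 days, roughly Weeks 15 to 21. An End of Treatment scan in that interval cannot become the Week 24 value, and the carry-forward rule does not pick it up. SAP 10.1 limits efficacy analysis to scheduled, centrally read images. That excludes unscheduled scans but not this one.

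**Who is affected.** All four conditions must hold:

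1. A Week 12 scan exists.
2. Treatment stops and the End of Treatment scan falls on about Days 106 to 146.
3. There is no Week 24 scan. Early stoppers otherwise stay on the visit calendar, imaging included, through Week 24.
4. The reason is other myelofibrosis therapy, splenic irradiation or splenectomy. After death or withdrawal of consent the End of Treatment visit is not required, so Week 12 is usually the latest scan anyway.

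**Size.** The documents attach no figure to this rule, so there is none to reproduce. The formula is:

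shift in an arm's mean = m × d / n

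Here m is the number of affected patients, d is the percentage points of reduction lost between Week 12 and End of Treatment, and n is the number in the mean. Protocol 11.7 gives n up to 50 per arm, SD about 20%, and 10% as the minimum meaningful reduction. Both m and d are assumptions.

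| m (of 50) | d = 25 | d = 35 | d = 60 |
|---|---|---|---|
| 2 | 1.0 | 1.4 | 2.4 |
| 5 | 2.5 | 3.5 | 6.0 |
| 10 | 5.0 | 7.0 | 12.0 |

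For scale, the standard error of an arm mean is 20/√50 = 2.8 points. The middle case, 5 × 35/50 = 3.5 points, exceeds one standard error and is about a third of the 10% threshold. With the 30 evaluable patients per arm in SAP 16, the same case gives 5 × 35/30 = 5.8 points against a standard error of 20/√30 = 3.7.

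**What each d means.** A loss of 35 points takes a patient from a 10% reduction to a 25% increase. A patient with exactly 35% reduction at Week 12 who then reaches the progression threshold has moved 35 + 25 = 60 points. That is the least a Week 12 responder can lose and still stop for volume progression. Losing responder status alone needs only an End of Treatment reduction below 35%.

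**Responder rate.** Each patient who is a responder at Week 12 but not at End of Treatment adds 1/50 = 2 percentage points to the carried-forward rate.

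**Opposite sign.** If the spleen was still shrinking when treatment stopped, d is negative. Five patients gaining a further 10 points (an assumption) give 5 × (−10)/50 = −1.0, so the carried-forward mean is too unfavourable.

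**The case against.** The case for leaving the rule alone has real substance.

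- **The analysis is supportive.** The SAP introduces it with "Additional supportive analyses include imputing missing Week 24 spleen volume". The main ≥35% proportion divides by all FAS patients (SAP 10.1), so a missing Week 24 scan cannot count as a response there. This stands.
- **The later scans are reported.** The End of Treatment summary gives percent reduction and the ≥35% proportion by arm, so regrowth is not hidden. This also stands, although that summary mixes time points and does not correct the carried-forward Week 24 figure.
- **The group is small by construction.** Most early stoppers are still to be scanned at Week 24. Regrowth already visible at Week 12 is carried forward as a poor value. No imaging is scheduled between Weeks 12 and 24, so volume progression in the gap would be found only on unscheduled or End of Treatment imaging.
- **SAP 10.1 can be read as letting the End of Treatment scan stand in for Week 24.** That sentence describes when scans are taken. The percent-reduction formula names only Weeks 12 and 24, so it does not rescue the rule.

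A reader might go further and infer that the rule always overstates benefit, favours the weakest dose, and flattens the dose-response on which selection rests. The documents do not support this. Toxicity stops can reverse the sign, and no counts by arm are given. Nothing says that carried-forward values feed the dose-response model: the PK/PD analysis is in a separate plan, and selection weighs efficacy, safety and PK/PD together.

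**Conclusion.** The point holds as a defect in one supportive analysis. As written, the carry-forward bypasses a later, scheduled, centrally read scan for a specific group of patients, and the SAP gives no reason for preferring Week 12. Where the patient stopped with regrowth, the carried-forward mean and ≥35% rate are too favourable. Where the patient stopped for toxicity during continued shrinkage, they can be too unfavourable.

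The illustrated shift for n = 50 runs from 1.0 point (2 patients losing 25) to 12.0 points (10 patients losing 60). Those counts and losses are assumptions. The documents do not allow the real number affected, or the net direction by arm, to be estimated. The finding does not call the main Week 24 responder analysis or the trial's conclusions into question. It is a cheap improvement.

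**What to change.** Replace the rule in SAP 12.1.1 with:

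*Missing Week 24 spleen volume is imputed with the latest scheduled, centrally read post-baseline volume, including the End of Treatment scan, taken before any splenic irradiation, splenectomy or new myelofibrosis therapy.*

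Apply the same latest-value principle to TSS in SAP 12.1.2, using the last evaluable diary window up to End of Treatment. The diary is completed daily, so the data should be there.

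If Week 12 was chosen on purpose, the minimum is to say so and show the latest-scan version beside it. There is no need to class everyone who stopped for progression as a Week 24 non-responder. That would override Week 24 scans that were actually observed, and it changes the estimand rather than repairing this rule.

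The cost is an edit to the SAP and a small programming change, with no new data collection. The carried-forward figures may come out slightly less favourable.

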- Sparse Sampling (all patients): End of Week 12 and End of Week 24: 30 minutes to 0 hours (predose), 4 hours (± 10 minutes), and 8 hours (± 15 minutes) postdose
- Dense Sampling (performed at selected sites until approximately 6 to 8 patients per dose arm have completed PK evaluation, at which point all further patients will have PK evaluated by sparse sample collection): Week 1 Day 1: 2 hours (± 5 minutes), 4 hours (± 10 minutes), 6 hours (± 15 minutes), and 8 hours (± 15 minutes) postdose and 24 hours postdose (within 30 minutes before the Day 2 dose), End of Week 12 and End of Week 24: 30 minutes to 0 hours (predose), 2 hours (± 5 minutes), 4 hours (± 10 minutes), 6 hours (± 15 minutes), and 8 hours (± 10 minutes), 6 hours (± 15 minutes), and 8 hours (± 10 minutes), 6 hours (± 15 minutes), and 8 hours (± 15 minutes)

The PK parameters, minimum concentration observed, maximum concentration observed, and area under the curve will be determined and summarized using descriptive statistics for each pacritinib dosage arm. Exposure-response analyses will be conducted on both safety and efficacy populations in the study. PD samples will be analyzed for biomarkers associated with the JAK/STAT pathway.

The maximum duration of trial participation for an individual patient will be approximately 24 weeks. The estimated duration of the entire study is approximately 2 years if the maximum number of patients are enrolled. The definition of End of Trial for the PAC203 study is Last Visit of the Last Subject (LVLS).

Number of Centers	Approximately 60 centers globally
Number of Patients	Approximately 150
Inclusion/ Exclusion Criteria	 Diagnosis and Inclusion Criteria PMF, PPV-MF, or PET-MF (as defined by Tefferi and Vardiman 2008) DIPSS Intermediate-1, Intermediate -2, or High risk (Passamonti et al 2010) Prior ruxolitinib treatment with failure to benefit or intolerance as defined by at least one of the following:

a. Treatment for ≥3 months with inadequate efficacy response defined as <10% spleen volume reduction by MRI or <30% decrease from baseline in spleen length by physical examination or regrowth to these parameters following an initial response: and/or
h Treatment for >28 days complicated by either
i Development of a red blood cell transfusion requirement (at least
2 units/month for 2 months)
 National Cancer Institute (NCI) CTCAE grade ≥ 3 AEs of thrombocytopenia, anemia, hematoma, and/or hemorrhage while being treated with a dosage of < 20 mg BID

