2.3.2 Secondary Objectives

The secondary objectives are as follows:

- 1. To examine the dose–response relationship for efficacy, as measured by spleen volume reduction (SVR) using MRI (preferred) or CT and TSS using the Myeloproliferative Neoplasm Symptom Assessment Form Total Symptom Score version 2.0 (MPN-SAF TSS 2.0)
- 2. To examine the dose-response relationship for safety with a focus on AEs of interest
- 3. To further characterize the pharmacokinetics (PK) and pharmacodynamics (PD) of pacritinib

3 Study Design

This is a dose-finding study in patients with PMF, PPV-MF, and PET-MF (DIPSS risk score of Intermediate-1 to High-Risk), who were previously treated with ruxolitinib. The study is designed to support a pacritinib dosage selection decision. Three dosages will be evaluated, with patients randomized 1:1:1 to pacritinib 100 mg OD, pacritinib 100 mg BID, or pacritinib 200 mg BID. Randomization will be stratified by baseline platelet count ($\leq 50,000/\mu$ L; >50,000/ μ L and $\leq 100,000/\mu$ L; and >100,000/ μ L). The most recent platelet count obtained prior to start of treatment will be the basis of stratification by baseline platelet count. Assigned treatment will continue until the patient experiences progressive disease, intolerable AEs, or withdraws consent, or until the assigned treatment arm is closed. No study treatment crossover will be allowed. All patients should complete all visit procedures through Week 24, including patients who stop pacritinib treatment or have protocol-defined progressive disease prior to Week 24, unless patient withdraws consent, dies, undergoes splenic irradiation or splenectomy, or initiates any nonprotocol-directed anti-myelofibrosis treatment. Following regulatory, Ethics or Institution Review Board approval of Amendment 6, study treatment for patients at and beyond the week-24 timepoint will terminate. Study assessments will cease following the End-of-Treatment or 30-day post (EOT) visit, as applicable. Patients who are benefiting from therapy as of study treatment termination may be allowed to continue receiving pacritinib under single patient expanded access or named patient programs at the investigator's discretion and subject to regulatory and Ethics or IRB approval.

The dosage selection process will be based on efficacy and safety parameters, including model-based dose response as described in Section 3.1.

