2.1.2 Secondary Objectives

The secondary objectives are as follows:

1. To examine the dose-response relationship for efficacy, as measured by spleen volume reduction (SVR) using MRI or CT and total symptom score (TSS) using the Myeloproliferative Neoplasm Symptom Assessment Form Total Symptom Score version 2.0 (MPN-SAF TSS 2.0; protocol Appendix 3)
2. To examine the dose-response relationship for safety with a focus on AEs of interest
3. To further characterize the pharmacokinetics (PK) and pharmacodynamics (PD) of pacritinib
4. To evaluate the long term efficacy and safety of pacritinib treatment

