3. SUMMARY OF STUDY DESIGN

This is a dose-finding study in patients with myelofibrosis who were previously treated with ruxolitinib, are highly symptomatic (DIPSS risk score of Intermediate-1 to High Risk), and have splenomegaly (assessed by physical examination). The study is designed to support a pacritinib dosage selection decision, the process of which will be based on pre-specified efficacy and safety parameters and assessed by an independent data monitoring committee (IDMC).

Spleen volume will be measured by MRI or CT at baseline and Weeks 12 and 24. Safety will be monitored with physical examinations, clinical laboratory assessments (including hematologic, chemistry, and coagulation testing), and cardiac monitoring (including ECG and echocardiogram testing); specified study treatment dosage modifications will be followed to address identified abnormalities. Adverse event data will be collected throughout the study.

Three dosages will be evaluated; pacritinib 100 mg QD, pacritinib 100 mg BID, and pacritinib 200 mg BID. During the study, the interim data will be reviewed by the IDMC for the determination of dropping treatment arm(s), which will be guided by

- The results of interim analyses evaluating the Bayesian predictive probability (BPP) of clinically meaningful SVR (details in section 7.4),
- Safety reviews, with occurrence of 2 treatment-emergent CTCAE grade ≥ 4 cardiac AEs or 2 treatment emergent CTCAE grade ≥ 4 hemorrhage AEs in any arm being of particular concern, and
- Other efficacy and safety measures.

Assigned treatment will continue for 24 weeks unless the patient experiences progressive disease, intolerable AEs, or withdraws consent, or until the assigned treatment arm is closed. Once an arm is closed, patients in that arm will discontinue the study. No study treatment crossover will be allowed. The maximum duration of trial participation for an individual patient will be approximately 3 years.

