7. DISPOSITION AND ENROLLMENT

Patient disposition will be presented as number and percentages of patients who were screened, randomized, completed the study, and discontinued the study. A completed patient will be one who has not been discontinued or withdrew consent from the study. Disposition will be summarized by treatment arm and for all study patients.

The number and percentage of patients prematurely discontinued from the study and the reasons for study discontinuation will be summarized for all randomized patients. The reasons for study termination include: withdrawal by patient, lost to follow-up, death, study termination by sponsor, physician decision and other reasons. In addition, the number of patients who discontinued treatment as well as the reasons for treatment discontinuation (adverse event, death, lost to follow-up, physician decision, study terminated by Sponsor, withdrawal by patient and other reasons) will be presented by treatment arm.

Study enrollment by country and region will be presented by treatment arm.

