10. EFFICACY VARIABLES

The primary efficacy variable for dosage selection is the percent reduction in spleen volume from baseline as measured by MRI or CT at Weeks 12 and 24.

Other supportive measures for evaluation as part of the dose-response relationship include

- the percentage of patients who achieve at least 35% reduction in spleen volume
- % TSS reduction from baseline, and
- the percentage of patients with at least 50% reduction in TSS.

The planned analyses for the efficacy endpoints of the study are detailed in the subsections below and will be performed in the full analysis set.

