10.1 Spleen volume (SPV)

Spleen volume will be measured by MRI (preferred) at baseline and Weeks 12 and 24 or end of treatment visit if imaging did not occur at the end of Week 24. Unscheduled imaging assessments may be performed at physician discretion if he/she considers disease-related symptoms to be worsening. Patients who cannot undergo MRI, or for whom MRI is not available will assess spleen volume by CT scan. However, for each patient, the same imagining modality will be used throughout the study. An independent radiologist, blinded to all patient and site identifiers as well as treatment assignments, will measure spleen volume. While images generated as part of unscheduled visits may be read locally if treatment discontinuation is being considered, only the scheduled centrally read images will be used for the efficacy analysis.

The percent reduction and the proportion of subjects with a $\geq 35\%$ spleen volume reduction will be computed as follows:

$$\text{SPV \% Reduction} = - \left(\frac{\text{Week 12 or 24 SPV} - \text{Baseline SPV}}{\text{Baseline SPV}} \right) * 100$$

$$\text{Proportion of subject with SPV reduction} \geq 35\% = \left(\frac{\text{Number of subjects with} \geq 35\% \text{ SPV reduction}}{\text{Number of subjects in the FAS population}} \right)$$

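### After Week 24 the spleen response rate keeps the full analysis set as its denominator, although Amendment 6 ends treatment and later scans, so the long-term rate falls with sponsor termination

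*SAP*

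**What the plan says.** **SAP, analysis rules.** Section 10 says the efficacy analyses "will be performed in the full analysis set". Section 10.1 defines the proportion with at least 35% spleen volume reduction with the denominator "Number of subjects in the FAS population". Section 12.1.1 lists the Week 12, Week 24 and End of Treatment summaries, including that proportion with its exact interval, and then states: "These analyses will be repeated for spleen volume measured after Week 24 in long term follow up". The analysis-windows table at the end of the SAP provides Week 36 and later windows for spleen volume. The only imputation rule is a supportive one that carries Week 12 to a missing Week 24. Nothing is written for later visits or for patients whose follow-up the sponsor ends.

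**Protocol, Amendment 6.** Section 3 says that, after approval, "study treatment for patients at and beyond the week-24 timepoint will terminate". The notes to the assessments calendar stop study assessments after the end-of-treatment visit or the visit 30 days later. Before that approval, section 7.1.1.1 plans scans every 3 months up to 2 years, but only for patients still taking pacritinib.

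**Duration, objective and completion.** The Protocol Synopsis says: "The maximum duration of trial participation for an individual patient will be approximately 24 weeks". SAP section 3 says: "The maximum duration of trial participation for an individual patient will be approximately 3 years". SAP 2.1.2 has a fourth objective, "To evaluate the long term efficacy and safety of pacritinib treatment", which protocol 2.3.2 does not list, although protocol 11.1 still names long-term efficacy measures. SAP section 7 says: "A completed patient will be one who has not been discontinued or withdrew consent from the study". It also lists termination by the sponsor among the reasons for leaving the study and for stopping treatment.

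**The concern.** A fixed FAS denominator suits Weeks 12 and 24, because the protocol asks every patient, on or off drug, to follow the visit schedule to Week 24, with few exceptions. After Week 24 that no longer holds. A patient may lack a Week 36 scan because treatment ended earlier for toxicity or progression, or because the sponsor stopped treatment when Amendment 6 was approved locally. The first says something about the drug. The second reflects the calendar. The literal rule treats both alike: in the denominator, never in the numerator.

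The continuous summaries have the opposite weakness. Percent reduction can only be computed from scans. After Week 24 these come only from patients still on drug, and protocol 3.3 takes patients off treatment once the spleen has grown by 25% or more. A reader could see the response rate fall while the mean reduction looks durable, with neither pattern caused by the drug. In the disposition table, a patient who finished 24 weeks and was then ended under Amendment 6 could be shown as not having completed.

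**Working it through.** **Plan's own figure.** The documents give no figure for long-term response, so there is none to reproduce on this point. The arm size of up to 50 comes from protocol 11.7. The 92% chance there of seeing at least one event at a true rate of 5% reproduces: 1 − 0.95^50 = 0.923. The factor derived below does not depend on arm size.

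**Inputs**
- N = 50 FAS patients per arm (protocol 11.7).
- r = share of the FAS that would be responders at the later visit. Assumed; 10%, 21.6% and 30% are shown. The middle value is the Week 24 rate for 200 mg BID in PERSIST-2 (16/74, protocol 1.3.4) and is used only as an illustration.
- f = share of those responders ended by the sponsor before the visit. Assumed; the documents give no value.

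**Formula.** Reported rate on the FAS = r × N × (1 − f) / N = r × (1 − f).

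**Example.** Take 10 responders among 50 (20%), all keeping their response.
- f = 30%: 10 × 0.7 = 7; 7/50 = 14%
- f = 60%: 10 × 0.4 = 4; 4/50 = 8%
- f = 90%: 10 × 0.1 = 1; 1/50 = 2%

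**Range.** Expected FAS rate:

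| r | f = 0 | 20% | 40% | 60% | 80% |
|---|---|---|---|---|---|
| 10% | 10.0% | 8.0% | 6.0% | 4.0% | 2.0% |
| 21.6% | 21.6% | 17.3% | 13.0% | 8.6% | 4.3% |
| 30% | 30.0% | 24.0% | 18.0% | 12.0% | 6.0% |

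With the same f in every arm, differences between doses shrink by the same factor. For 30% against 10%, a gap of 20 points becomes 18.0 − 6.0 = 12 points at f = 40%.

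**Effect of the denominator.** Suppose the sponsor ends 20 of 50 patients (40%), nobody else has stopped, and 6 responders remain. On the FAS this is 6/50 = 12.0% (exact 95% CI 4.5% to 24.3%). Among the 30 not ended by the sponsor it is 6/30 = 20.0% (7.7% to 38.6%). If some of those 30 had stopped earlier for other reasons, dividing by scanned patients only would give a still smaller denominator and a higher rate. The choice of denominator therefore has to be written down.

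**The case against.** The strongest reply is that the SAP never calls a sponsor-ended patient a non-responder. The percent-reduction formula in 10.1 names only Weeks 12 and 24, and 12.1.1 speaks of volume measured after Week 24, which can be read as observed scans only. This stands as a limit: counting such patients as failures is a consequence of the literal FAS denominator, not a stated rule. It does not remove the point, because two defensible readings give different rates and neither is labelled.

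Safeguards also exist. Scans made before local approval of Amendment 6 remain. An end-of-treatment scan is required if treatment does not end at Week 24, and SAP 12.1.1 reports response at End of Treatment from that scan or the last one on treatment. A responder ended by the sponsor is still a responder in that table. Summaries carry counts, and SAP 7 already tabulates sponsor termination as a reason. What is missing is a split between ending before and after a completed Week 24 visit. Whether Amendment 6 patients would be coded as not completed is an inference.

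Three stronger readings are tempting, and the documents do not support them.
- **Later-enrolling arms look worse.** Patients are randomised to the three arms concurrently, 1:1:1 in permuted blocks of 3 within strata (SAP 4), and no arm closure is reported. Exposure to the cut-off should be similar by design.
- **The dose decision is distorted.** The primary efficacy variable is at Weeks 12 and 24, the decision is taken once all patients have reached Week 24 or left the study, and no hypothesis is tested.
- **SAP objective 4 should be deleted.** Protocol 11.1 still plans long-term efficacy. Its long-term spleen volume measure is percent reduction; the long-term 35% proportion comes from SAP 12.1.1.

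**Conclusion.** The point holds for the descriptive summaries after Week 24. Applied as written, the FAS denominator multiplies the long-term response rate by (1 − f), so a true 20% would be reported as 14%, 8% or 2% if 30%, 60% or 90% of responders were ended by the sponsor. These shares are assumptions, and the example further assumes that every responder keeps the response. The continuous summaries cover only patients remaining on drug and cannot correct the picture. All arms are affected. The Week 12, Week 24 and End of Treatment results are not, and no arm-specific bias is shown. The mismatch over participation length and the long-term objective is plain in the text and needs no assumption. Severity is minor to moderate.

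**What to change.** 1. **SAP 10.1 and 12.1.1.** Keep the FAS denominator for Week 12, Week 24 and End of Treatment. For each later visit, use FAS patients whose scheduled visit date precedes sponsor termination under Amendment 6 at their site. Within that group, keep patients who stopped earlier for other reasons in the denominator as not responding. Show the number ended by the sponsor. Membership then depends on entry and termination dates, not on response. Counting earlier stoppers as not responding is a choice of estimand and should be stated as one.
2. **Post-Week-24 means.** Label them as describing patients remaining on treatment, with the number remaining.
3. **SAP 7.** Report sponsor termination after a completed Week 24 visit separately from premature discontinuation.
4. **SAP 2.1.2 and 3.** Reconcile objective 4 and the 3-year participation with the protocol's 24 weeks and with the long-term measures in protocol 11.1.

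The cost is SAP wording and one derived flag, built from scheduled visit dates and each site's Amendment 6 termination date. The recorded reason for ending treatment identifies the sponsor-ended patients. The drawback is small long-term denominators with wide intervals, which limits these results to description.
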